#### *Role of Intravenous Fat Emulsion on PN Associated Liver Disease*

Recent evidence demonstrates that lipids are metabolized differently depending on their route of administration. Enteral lipids are absorbed by the enterocyte in the small bowel mucosa in the form of a micelle and packaged into chylomicrons which are released into the portal venous system for ultimate uptake and disposal in the liver. Once in the bloodstream, these particles rapidly acquire apolipoproteins from circulating high-density lipoproteins and can subsequently be metabolized by the liver. The emulsified particles of commercially made and intravenously administered lipid emulsions, such as Intralipid®, mimic the size and structure of chylomicrons, but differ in their content. In contrast to chylomicrons, artificial lipid particles primarily contain essential fatty acids and omega-6 triglycerides and are devoid of cholesterol or protein. Recent studies suggest that these omega-6 fatty acid-containing emulsions are dependent on lipoprotein lipase, apolipoprotein E, and low-density lipoprotein receptors for clearance, and are metabolized with less lipolysis and release of essential fatty acids than are chylomicrons. In fact, it appears that they may be cleared as whole particles by tissues other than the liver.(16) These factors may account for the increased incidence of steatohepatitis associated with the intravenous administration of Intralipid®.

The mechanism of clearance of omega-3 fatty acid containing lipid emulsions is unknown, but appears to be largely independent of the pathways identified above (17). Furthermore, omega-3 fatty acid solutions have been shown to decrease de novo lipogenesis (18), prevent or attenuate PN-induced hepatosteatosis in rats (19) and guinea pigs and ameliorate the severity of high-fat diet-induced hepatosteatosis in rats (20). In addition, omega-3 fatty acids can interfere with the arachidonic acid pathway of inflammation (18, 21). They can displace arachidonic acid from tissue fatty acid pools, thereby reducing the availability for eicosanoid-synthesizing enzymes and inflammation (21). Table 1 summarizes the composition of Intralipid® and Omegaven® fat emulsions.

#### *Rationale for Omegaven® Treatment*

Unlike conventional intravenous fat emulsions, Omegaven® is comprised solely of fish oils containing primarily omega-3 fatty acids. Animal studies have shown that IV fat emulsions such as fish oil that are high in eicosapentaenoic and docosahexaenoic acid reduce impairment of bile flow as seen in cholestasis caused by conventional fat emulsions(19,20). We hypothesize that by administering Omegaven® in place of conventional phytosterol/soybean fat emulsions, that the cholestasis may be reversed and patients will be able to be maintained on adequate PN until they are able to ingest adequate nutrition enterally.

[name], Department of Surgery, Children's Hospital & Medical Center  
[name], Department of Surgery, Children's Hospital & Medical Center  
[name], Pediatric Research Office, Dept. of Pediatrics, UNMC  
[name], Department of Biostatistics, College of Public Health, UNMC

*Preliminary Studies/Progress Report*  
*Animal Studies*

In initial studies conducted at Children's Hospital Boston, it was hypothesized that the development of PNALD may be dependent on both the route and quantity of fat administration and that omega-3 fatty acids would prevent or reduce de novo lipogenesis and the subsequent liver injury independent of the route of administration. Specifically, they characterized a previously established murine model of PN-associated liver injury to investigate whether enteral lipid administration would protect against the development of steatohepatitis in PN-dependent animals. This murine model of enteral PN-induced steatohepatitis is largely due to a high carbohydrate load and essential fatty acid deficiency. Although this model is not replicative of the clinical setting, it is a model that maximizes liver steatosis. In this model, mice are treated with oral PN for 19 days before being sacrificed. These animals develop severe fatty liver changes demonstrated by MRI spectroscopy and histology (H&E, PAS, and oil red O staining), and also have biochemical changes consistent with liver injury (elevated alkaline phosphatase and serum transaminases). Experimental groups were supplemented with Intralipid® by several routes of administration including orally, intravenously, and subcutaneously. Other groups were also supplemented with omega-3 fatty acids (Omegaven®) by the same routes of administration. In this study they found a consistent pattern of protection against PN-associated steatohepatitis by administering enteral Intralipid® (22). In mice that received the highest dose of enteral Intralipid®, there was a marked decrease in the extent of overall liver injury as measured by gross inspection, histologic analysis, liver fat content, and serum liver enzyme levels. In all areas of this investigation, mice treated with enteral lipid most closely resembled the control mice that did not receive PN as part of the experimental protocol. These results were in complete contrast to the extensive fatty infiltration and evidence of hepatic injury found in mice that received PN without lipid supplementation as well as in mice that received PN with intravenous Intralipid®. Mice receiving intravenous Intralipid® had the most severe liver changes. Both groups of animals developed marked hepatic steatosis with macrovesicular fatty infiltration and significant elevations in spectroscopic liver fat content and serum transaminase levels. In addition, the effect of enteral Intralipid® supplementation appeared to be dose-dependent; mice receiving one-third the dose of enteral Intralipid® showed improved liver histology but still demonstrated a moderate degree of liver injury by spectroscopy and serum liver function tests. The nutritional model employed in this study provided all experimental mice with enteral PN solution ad libitum. In this way, mice were not force-fed PN and self-regulated their PN intake by demands for growth and energy. Importantly, all mice gained weight throughout the 19-day protocol, and there were no differences in weight gain parameters between the groups. The PN solution was a typical pediatric stock formula mixed at our institution containing 20% dextrose and 2% amino acids. Each milliliter of this formula provides 0.2 g (0.68 kilocalories) of dextrose and 0.02 g (0.08 kilocalories) amino acid. As the daily intake per animal of PN averaged 15 ml, mice were ingesting approximately 11.4 kilocalories/day and 456 kilocalories/kg/day. This caloric load is similar to the established dietary energy needs of the mouse (23). The parenteral fat source used in this study was Intralipid® 20% (Baxter, Deerfield, Illinois), which is a soybean oil-based emulsion. Each milliliter of this emulsion contains 0.2 g (2.0 kcal) of fat. We recognize that the model may not completely match the clinical, human, setting of intravenous PN-administration; however, our goal was to produce a fatty liver with biochemical evidence of injury.

In a second set of experiments, the same murine model was used to determine whether Omegaven® (Fresenius- Kabi, Bad Homburg, Germany), a commercial fish oil fat emulsion

[name], Department of Surgery, Children's Hospital & Medical Center  
[name], Department of Surgery, Children's Hospital & Medical Center  
[name], Pediatric Research Office, Dept. of Pediatrics, UNMC  
[name], Department of Biostatistics, College of Public Health, UNMC

available in Europe, would prevent fatty liver changes by enteral or parenteral routes of administration, and to determine the serum fatty acid profile of these animals. Animals receiving Omegaven® via the oral and intravenous routes had completely normal livers on histology and MRI spectroscopy revealed normal liver fat content. Liver functions tests in orally treated animals were also within the norm, while there were minimal elevations in intravenously treated groups. There was no fatty acid deficiency in these groups as determined by Mead acid (5,8,11-Eicosatrienoic acid) levels in the serum fatty acid analysis. Mead acid is the only polyunsaturated fatty acid of note produced de novo by animals and only accumulates under the conditions of essential fatty acid deficiency. Furthermore, arachidonic acid levels were low in Omegaven® treated animals consistent with previous reports. In a third set of experiments, mice were made severely fatty acid deficient. These mice were treated for 10 days with Omegaven® and had complete reversal of their fatty acid deficiency.

Similarly, other investigators studied livers in a newborn pig model and showed that intravenous administration of fish oil, which consists primarily of omega-3 fatty acids, reduced parenteral nutrition-induced cholestasis (22). However, the study was only 3 weeks in duration and long-term effects from administration of omega-3 fatty acids alone were not evaluated. In fact, the idea that one could remove an essential fatty acid from the standard regime of nutritional support by PN has not been accepted. It has been thought that reduction of an essential fatty acid, such as omega-6, during long-term therapy would result in fatty acid deficiency and deterioration of the health of the patient. [name] experience to date, as discussed below, demonstrates that the use of Omegaven® as monotherapy does not result in the development of essential fatty acid deficiency and it can actually be used as monotherapy to treat this deficiency state.

#### *Preliminary Safety and Efficacy Data for Use of Omegaven® in Other Diseases*

Omegaven® has been used for over 10 years as an adjunct to conventional fat emulsions. According to current data, an increase in the proportion of omega-3 fatty acids is thought to optimize nutrition in general, but in particular benefit patients whose underlying disease might benefit from an increase in omega-3 fatty acids. An adequate intake of omega-3 fatty acids results in anti-inflammatory and immunomodulatory effects that are protective in nature from inflammatory tissue damage, capillary permeability, and improved immunological resistance. It may also reduce the risk of thrombosis and increase microvascular perfusion due to its anti-aggregatory and vasodilatory effects.

In Europe and Asia, the use of parenteral omega-3 fatty acids has been used in the following adult patient populations (24-28):

- post traumatic and post surgical patients
- patients experiencing early stages of sepsis/SIRS
- patients at risk of hyperinflammatory processes
- patients with inflammatory bowel disease (Crohn's disease, ulcerative colitis)
- patients with inflammatory skin diseases (psoriasis, atopic eczema)

The dosing used in these patients was 0.1 g (1ml) to a maximum of 0.2 (2ml) /kg body weight. The infusion rate used did not exceed 0.5ml/kg/body weight/hour. Since it was intended to be infused in combination with conventional fat emulsions, the total fat intake was limited to 10-20% as fish oil. The duration of administration did not exceed 4 weeks.

[name], Department of Surgery, Children's Hospital & Medical Center  
[name], Department of Surgery, Children's Hospital & Medical Center  
[name], Pediatric Research Office, Dept. of Pediatrics, UNMC  
[name], Department of Biostatistics, College of Public Health, UNMC

### *Preliminary Safety and Efficacy Data for Use of Omegaven® in Infants*

Pediatric experience with Omegaven® is limited to [name] clinical trial at Boston Children's Hospital and 2 other unpublished clinical trials. These other trials were performed in Germany and Taiwan (29). The German study was a controlled, randomized, open parallel-group clinical study to investigate whether or not omega-3 fatty acids could be incorporated into the plasma phospholipids of very low birth weight preterm infants. In this 7-day safety trial, Omegaven® use was evaluated on the basis of clinical, laboratory, and antioxidant parameters and lipid metabolism. Treatment was started on day 3-5 of life and continued for a total of 7 days. Patients received Omegaven® plus conventional soybean fat emulsion or soybean emulsion alone. The maximum dose of Omegaven® in the study was 0.2 gm/kg/day. The study concluded that the Omegaven® was well tolerated in this group of preterm infants in respect to both hematological and biochemical parameters. The incidence of reported adverse events between both study groups was similar. The eicosapentaenoic acid (EPA) content of plasma phospholipids increased significantly in the Omegaven® arm, with the proportion of EPA to the total fatty acids reaching almost three times the baseline value. The sum of omega-3 fatty acids showed a significantly greater increase in the Omegaven® group compared to the conventional treatment arm.

The Taiwanese study was a single center, controlled, open-labeled study conducted to investigate the safety of parenteral administration of Omegaven® in preterm infants. The group of 20 infants were randomized to one of two treatment groups; one consisting of Omegaven®/conventional lipids and the other consisting of conventional lipids alone. The average dose of Omegaven® in the treatment group of this 14-day study was 0.13 + 0.02 g/kg/day. There were no significant differences between the two groups with regard to body weight and length. Similarly, there was no significant difference in the hematological or biochemical parameters. There were no adverse events that were attributable to Omegaven® use. It was concluded that Omegaven® was well tolerated in these preterm infants.

## **DESIGN AND METHODS**

### **A. Study Design**

Assessment of the effect of treatment will be based on a non-randomized, open-labeled, prospective study of intravenously administered Omegaven® fat emulsion to determine safety and preliminary efficacy in the treatment of PN associated liver injury.

### **B. Patient Selection and Inclusion/Exclusion Criteria**

After the diagnosis of PNALD is made, patients who are followed by the Department of Surgery, in conjunction with the patient's primary physician, will contact [name] and an evaluation will be performed. Cases may also include referrals of patients with PNALD from other healthcare facilities or self-referrals upon transfer to our institution. If the patient's parents or guardians agree to participate in the study, informed consent will be obtained. The history of present illness and past medical history will be reviewed with the guardian and pertinent demographic and medical information will be recorded on data collection forms. This form will be used to record all laboratory results, nutritional history, and descriptions of any liver biopsies performed.

Though most patients receiving parenteral nutrition do not develop end stage liver disease, there is a small percentage of patients, typically infants and children on prolonged courses of

[name], Department of Surgery, Children's Hospital & Medical Center  
[name], Department of Surgery, Children's Hospital & Medical Center  
[name], Pediatric Research Office, Dept. of Pediatrics, UNMC  
[name], Department of Biostatistics, College of Public Health, UNMC

parenteral nutrition, who do go on to develop fulminate liver failure. The study population of this protocol is limited to patients felt to fulfill any one of the following conditions:

- a) The patient will be PN dependent and at risk for significant hepatic injury due to prolonged use of parenteral nutrition.
- b) Have significant hepatic dysfunction due to parenteral nutrition despite utilization of all conventional therapies.

**Inclusion Criteria:**

1. Patients will be PN dependent (unable to meet nutritional needs solely by enteral nutrition) and are expected to require PN for at least another 30 days.
2. Patients considered eligible for study participation must have parenteral nutrition associated liver disease (PNALD) as defined as a direct bilirubin of  $\geq 2$  mg/dl on at least the last two consecutive measures or by histology and/or currently on Omegaven through another protocol and unable to remain on that protocol due to transfer to our institution. Other causes of liver disease should be excluded. A liver biopsy is not necessary for treatment.
3. The patient must have utilized standard therapies to prevent the progression of his/her liver disease including surgical treatment, cyclic PN, avoiding overfeeding, reduction/removal of copper and manganese from PN, advancement of enteral feeding, and the use of ursodiol (i.e., Actigall®).
4. Patients ages birth up to and including 18 years of age.

**Exclusion Criteria:**

1. Pregnancy
2. Other causes of chronic liver disease (Hepatitis C, Cystic fibrosis, biliary atresia, and alpha 1 anti-trypsin deficiency.)
3. Enrollment in any other clinical trial involving an investigational agent (unless approved by the designated physicians on the multidisciplinary team)
4. The parent or guardian or child unwilling to provide consent or assent

In rare instances, patients diagnosed with PNALD may later be found to have liver disease due to other causes in addition to the use of PN (i.e., inborn errors of metabolism, viral infections). Such causes may not be known at the time of enrollment; however, these patients will be excluded upon identification.

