**Patients will be withdrawn from the study for any of the following:**

- a) Toxicity considered unacceptable by the Principal Investigator (i.e. Evidence of burr cell anemia (reported toxicity); Continued lipid intolerance (triglyceride >200) despite dose reduction attempts and administration modification; evidence of coagulopathy (INR > 2.0)).
- b) Patient/guardian requests to discontinue treatment and/or observation for any reason.
- c) A suitable organ has been located and the patient is able to undergo a liver or liver/intestinal transplant.
- d) Decision by the Principal Investigator that termination is in the patient's best medical interest.
- e) Patient is lost to follow up.

In the event that a patient is withdrawn from the protocol, study staff will document the date of withdrawal, the reason for withdrawal, and the results of all measurements of interest made up to date of withdrawal.

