## **DATA ANALYSIS PLAN**

Using graphical methods (including boxplots) and descriptive statistics, we will assess assumptions required for validity of statistical methods and presence of outliers. Continuous variables will be summarized via means (and standard deviations) or medians (and interquartile ranges, when appropriate. When appropriate, variables will be transformed.

Primary analyses of the primary outcome will be based on the intention-to-treat analysis i.e., patient will be considered receiving Omegaven® throughout the whole follow-up period, regardless of temporary discontinuation of treatment due to infections or other causes.

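### Children found after enrolment to have another liver disease are excluded, but the protocol does not say how they are analysed, which can bias time to normalisation in favour of Omegaven

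*Protocol*

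**What the plan says.** Four places in the protocol bear on this point.

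- **Section B, Exclusion Criteria.** After the numbered list, the text adds: "In rare instances, patients diagnosed with PNALD may later be found to have liver disease due to other causes". The examples are "i.e., inborn errors of metabolism, viral infections", and the other cause is described as additional to the use of PN. The rule follows: the cause may be unknown when the child enters, but "these patients will be excluded upon identification".
- **Data Analysis Plan.** "Primary analyses of the primary outcome will be based on the intention-to-treat analysis". The protocol explains this as follows: "patient will be considered receiving Omegaven® throughout the whole follow-up period, regardless of temporary discontinuation of treatment due to infections or other causes".
- **Section G, withdrawal list.** Under "Patients will be withdrawn from the study for any of the following" it gives five reasons. A newly found liver disease is not named. Reason d), the Principal Investigator's judgement of the patient's best medical interest, could cover it. For withdrawn patients, the date, the reason and all measurements up to withdrawal are documented.
- **Analysis of Efficacy of Omegaven.** The primary efficacy outcome is time from baseline to bilirubin normalisation, estimated by Kaplan-Meier. Children who die or are transplanted before normalising are given an infinite time, because they have the worst outcome and should not be censored. Children excluded for another diagnosis are not mentioned.

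Section A describes a "non-randomized, open-labeled, prospective study of intravenously administered Omegaven® fat emulsion".

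**The concern.** The rule acts after enrolment, and possibly after treatment, on information that need not have existed at baseline: a viral infection can arise after the first infusion. The children it removes still have PN-associated disease, since the other cause is additional, so they remain close to the target population.

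The difficulty is that removal may depend on outcome. When bilirubin does not fall, clinicians have a reason to look for another explanation; when it normalises, they have less. In an open-label study those ordering the tests know the response. The Reversal Study Lab Schedule also keeps non-responders under closer observation: apart from the inpatient PN profile, testing on Omegaven moves from weekly to monthly once direct bilirubin is below 2 mg/dL. Those laboratory panels do not diagnose other liver diseases, but they show that contact is closer while bilirubin is high.

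If the excluded children are mostly non-responders, leaving them out, or censoring them as if their prospects matched those still at risk, overstates how often and how fast bilirubin normalises. In a cohort this small a few children matter.

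**Working it through.** No figure in the protocol is in dispute. The check asks what each reading of the rule does to the estimate.

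**Inputs.** Cohort sizes of 20, 25 and 30 come from the power section (Table 4). The following are assumptions, because the protocol gives no figures: 60% of all treated children normalise, k = 1 to 3 children are excluded, and all of them are non-responders. The range for k is kept small because the protocol calls the cases rare.

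**Reading 1: excluded children leave the analysis.** With r normalising among n, the proportion moves from r/n to r/(n − k).

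| n | r | All kept | k = 1 | k = 2 | k = 3 |
|---|---|---|---|---|---|
| 20 | 12 | 60% | 12/19 = 63.2% | 12/18 = 66.7% | 12/17 = 70.6% |
| 25 | 15 | 60% | 15/24 = 62.5% | 15/23 = 65.2% | 15/22 = 68.2% |
| 30 | 18 | 60% | 18/29 = 62.1% | 18/28 = 64.3% | 18/27 = 66.7% |

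The shift runs from 2.1 points (n = 30, k = 1) to 10.6 points (n = 20, k = 3).

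The time scale moves too. Take n = 25, no other censoring, and the median as the first time the Kaplan-Meier curve is at or below 0.5. With all children kept, the curve stands at 13/25 = 0.52 after 12 normalisations and 12/25 = 0.48 after 13, so the median is the 13th normalisation time. With three non-responders dropped, it reaches 11/22 = 0.50 at the 11th.

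**Reading 2: excluded children are kept but censored at exclusion.** Again n = 25, with 15 normalising and three non-responders censored:

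- Censored before any child normalises: 1 − 7/22 = 68.2%, the same as dropping them.
- Censored after 10 of the 15 have normalised: 15 of 25 remain, three leave, and 5 of the remaining 12 normalise. The estimate is 1 − (15/25)(7/12) = 1 − 0.35 = 65.0%.
- Censored after the last normalisation: 1 − 10/25 = 60%, no effect.

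So censoring gives 60% to 68.2%, depending on when exclusion happens.

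**Reading 3: excluded children stay at risk, as deaths and transplants do.** The estimate is 15/25 = 60%. The protocol's own reasoning for deaths and transplants points this way, but its wording does not extend to excluded children.

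**Safety, if treated children were left out of the counts.** Suppose two children have an event, and one of them is dropped. The rate goes from 2/20 = 10.0% to 1/19 = 5.3%, from 2/25 = 8.0% to 1/24 = 4.2%, or from 2/30 = 6.7% to 1/29 = 3.4%. Each is roughly a halving. Separately, the main safety period starts 30 days after treatment begins, so a child who leaves the study before then adds nothing to it.

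**The case against.** The strongest reply is that the sentence closes an eligibility list and says only that the child is excluded. It does not say whether from treatment, follow-up or analysis, and nothing in the Data Analysis Plan removes the data. A reader might infer that the protocol contradicts intention-to-treat and discards non-responders together with their adverse events. The documents do not support that:

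- The protocol explains its intention-to-treat rule only through temporary discontinuation, so there is no literal conflict.
- Section G has adverse events assessed and reported from first infusion until study exit, and keeps measurements up to withdrawal. Adverse event reports also go to the DSMB chair. Loss of events already recorded is possible but not stated.
- Outcome-dependent work-up is plausible, not shown. Other causes are to be ruled out at entry, screening includes a multidisciplinary review, and no passage ties diagnostic work-up to bilirubin response.

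A reader might also assume larger numbers. Five exclusions among 25 would give 15/20 = 75%, but that removes a fifth of the cohort and half of the ten assumed non-responders, which does not fit cases called rare.

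All of this stands and limits the claim. It does not remove it. A statistical analysis plan would commonly define analysis populations, but here the protocol itself fixes a post-enrolment exclusion. Read as removal, the rule can favour Omegaven; read as leaving the study, it leaves open a censoring that can do the same. That efficacy is labelled preliminary and primary safety is descriptive lowers the stakes, but does not make the estimates unbiased.

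**Conclusion.** The point holds as a failure to reconcile the exclusion rule with the intention-to-treat statement, the withdrawal list and the time-to-normalisation rule. Dropping non-responders, or censoring them before others have normalised, raises the estimated rate and tends to shorten the estimated time. With an assumed 60% rate and 1 to 3 excluded non-responders, the inflation is about 2 to 11 percentage points across 20 to 30 children, and 2.5 to 8.2 points at 25. These are illustrations: the rate, the number excluded and their all being non-responders are assumed, and the bias shrinks if exclusions are unrelated to response or happen late. The protocol should be corrected, since even rare exclusions count at this cohort size.

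**What to change.** In the Data Analysis Plan, state that:

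1. Every child who received any Omegaven stays in the primary efficacy analysis and in all safety analyses, with all data collected.
2. For time to normalisation, a child excluded before normalising is not treated as non-informatively censored at exclusion. Bilirubin follow-up continues where possible; otherwise the child is counted as not normalised.
3. The analysis without children who have an alternative diagnosis is a sensitivity analysis only, limited to conditions present before the first infusion.

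The Exclusion Criteria and the section G withdrawal list must also be reconciled on what happens to these children. Whether they stop treatment is a clinical matter on which this review takes no position.

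The cost is a few sentences and one extra table. The headline rate may be slightly lower, and counting a child without further bilirubin data as not normalised is conservative if that child would have normalised later.
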